## **PRÉCIS**

## **Background:**

- Adenosquamous carcinoma of the pancreas (ASCP) is a highly aggressive variant of pancreatic ductal adenocarcinoma (PDA), the most common type of pancreas cancer.
- ASCP is estimated to account for 0.5-4% of the 55,000 people who are diagnosed with pancreatic cancer in the U.S. each year, making it a very rare tumor type.
- No prospective clinical trials specific to ASCP have ever been performed.
- Preclinical data in ASCP models indicate that an activated superenhancer network drives epigenetic changes which cause the prognostically unfavorable squamous differentiation.
- Genomic analysis of ASCP tumors identifies frequent amplification of MYC.
- Minnelide is a small molecule anti-superenhancer drug that inhibits MYC.
- The recommended dose of Minnelide has previously been established through clinical testing for other indications.

## **Primary Objective:**

• To determine the single agent antitumor activity (disease control rate) of the antisuperenhancer agent Minnelide in participants with advanced, previously treated ASCP

## **Eligibility:**

- Age  $\geq$  18 years
- Histologically confirmed ASCP or high suspicion for ASCP based on histologic analysis for squamous markers
- Participants with metastatic or locally advanced unresectable disease and progression on at least 1 prior treatment regimen

## **Design:**

- This is a phase II single cohort clinical trial with one arm.
- The number of evaluable participants needed for the primary endpoint is 25; maximum accrual set at 55 participants (accounting for screen failures and inevaluable participants).
- Initial participants will receive Minnelide at 2 mg/day PO on Days 1-21 of a 28 day cycle. Later participants will receive a higher dose of 2.5 mg/day PO on the same schedule.
- Treatment will be continued for up to 12 cycles (1 year) in the absence of disease progression or unacceptable toxicity.
- Treatment response will be assessed by imaging every 2 cycles (8 weeks).
- Optional tumor biopsies will be requested mid-cycle 1 and at time of progression.
- A disease control rate of  $\geq 40\%$  in this highly refractory population would constitute a positive study. Up to 12 participants will treated be initially. If 3 of the 12 participants have a response, then up to 13 additional participants will be entered to determine the true response rate.

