## 10 STATISTICAL CONSIDERATIONS

### 10.1 OBJECTIVES AND ENDPOINTS

OBJECTIVES	ENDPOINTS	JUSTIFICATION FOR ENDPOINTS
Primary		
To determine the single agent antitumor activity (disease control rate) of the anti-superenhancer agent Minnelide in participants with advanced, previously treated ASCP	Assess disease control rate in the study population, where disease control = best response of CR, PR or at least 16 weeks of stable disease	Establishing disease control in 8 or more of 25 participants with advanced previously treated ASCP would be considered clinically significant.
Secondary		
Determine Minnelide safety in participants with advanced, previously treated ASCP	Identify Adverse Events of grade 2 and above (per CTCAE criteria, version 5.0) related to Minnelide that occur from start of treatment to 30 days after last treatment.	Descriptive endpoint to assess toxicity profile of the study drug in this population.
	Assess rate of Serious Adverse Events related to Minnelide that occur from start of treatment to 30 days after last treatment.	
Assess alternative measures of anti- tumor activity	Determine median time until disease progression, switch to a new systemic treatment or death in the treated population. Data cut-off will occur 1 year after last Minnelide treatment.	Descriptive endpoints that may help to determine sample size needed for future Phase 3 study
	Determine median time until death in the treated population. Data cut-off will occur 1 year after last Minnelide treatment.	
	Determine objective response rate of Minnelide.	

OBJECTIVES	ENDPOINTS	JUSTIFICATION FOR ENDPOINTS
Exploratory		
Identify factors that influence participant response to treatment through detailed molecular analysis of participant tumor, serum and blood cell samples acquired at baseline, on-treatment and at time of progression	For each patient with available samples, we will describe the following properties and consider associations with patient response to therapy:	These endpoints have been selected to help understand why the drug may or may not work, to allow better design of future studies in this patient population.
	Tumor genetic mutations at baseline and at time of progression	Do specific genetic profiles give a patient higher or lower likelihood or response? Does treatment change mutational profile?
	Treatment-related change (between pre-treatment baseline and ~C1D15) in:	

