#### 10.3 SAMPLE SIZE DETERMINATION

The primary objective of this trial is to determine if the CR, PR and SD > 16 weeks (clinical benefit) rate will be adequate using Minnelide without stratification for dose. The trial will be conducted using a Simon optimal two-stage phase II trial design [20][19] to rule out an unacceptably low clinical benefit rate of 20% (p0=0.20) in favor of an improved clinical benefit rate of 40% (p1=0.40). With alpha=0.10 (probability of accepting a poor treatment=0.10) and beta=0.20 (probability of rejecting a good treatment=0.20), the first stage will enroll a total of 12 evaluable participants. If 0-2 of these 12 participants have clinical benefit, then no further participants will be accrued. If 3 or more of the first 12 participants have clinical benefit, then accrual would continue until a total of 25 evaluable participants have been enrolled. As this is a rare participant population, trial accrual may continue for up to 15 participants while this determination is being made, but no new participants may be accrued to the trial once it is known that this criteria has not been met. If single agent activity is insufficient to meet criteria for study continuation, consideration will be given to exploring combination therapy including Minnelide in this population. If there are 3-7 participants with clinical benefit out of 25 participants, this would be an uninterestingly low clinical benefit rate. If there are 8 or more of 25 (32%) who experienced clinical benefit, this would be sufficiently interesting to warrant further study in later trials. Under the null hypothesis (20% clinical benefit rate), the probability of early termination is 55.8%.

It is expected that approximately one participant may initiate treatment on this trial every 1-2 months; thus, accrual to the trial may be completed in 3 years. In order to allow for screen failures and a small number of inevaluable participants, the accrual ceiling will be set at 55 participants.

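### The précis calls the study positive at a disease control rate of 40% or more (10 of 25), while sections 10.1 and 10.3 set the bar at 8 of 25 (32%)

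*Combined protocol and SAP*

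**What the plan says.** **Précis, Design.** A disease control rate of 40% or more "in this highly refractory population would constitute a positive study". The same list states: "The number of evaluable participants needed for the primary endpoint is 25". It prints no success count. Its first-stage gate reads: "If 3 of the 12 participants have a response", after which up to 13 more participants enter.

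**Section 10.1, primary endpoint row.** "Establishing disease control in 8 or more of 25 participants with advanced previously treated ASCP would be considered clinically significant".

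**Section 10.3.** The design is a Simon optimal two-stage design with a null rate of 20%, "in favor of an improved clinical benefit rate of 40% (p1=0.40". The error rates are set as follows: "With alpha=0.10 (probability of accepting a poor treatment=0.10) and beta=0.20". Accrual stops if 0 to 2 of the first 12 evaluable participants have clinical benefit and continues to 25 if 3 or more do. On the final count: "If there are 3-7 participants with clinical benefit out of 25 participants, this would be an uninterestingly low clinical benefit rate". The success region follows: "If there are 8 or more of 25 (32%) who experienced clinical benefit", which the section says is enough to justify later trials. The stated probability of early termination under the null is 55.8%.

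All of these statements concern one endpoint, called disease control in some places and clinical benefit in others (CR, PR, or stable disease for 16 weeks), and the same 25 evaluable participants.

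**The concern.** The combined document holds two success criteria for its primary endpoint. Since 0.40 × 25 = 10, the précis asks for 10 of 25. Sections 10.1 and 10.3 ask for 8. Results of 8/25 (32%) and 9/25 (36%) fall between the two: section 10 counts them as success and the précis does not call them positive.

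The 40% in the précis equals the alternative rate p1 in 10.3. That is the true rate at which the design is meant to have 80% power. The cut-off on the observed rate lies lower, at 32%. The précis appears to have turned p1 into a cut-off.

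A statistician working from section 10 has one rule. The risk is that someone working from the précis misreports the primary result. It is made worse because section 10.5.2 plans only an estimate with a 95% confidence interval, so the success label depends entirely on the count. With two bars in the document, the label could be chosen after the count is known.

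**Working it through.** **Inputs.** From 10.3: n1 = 12, stop if 2 or fewer, N = 25, success at 8 or more, p0 = 0.20, p1 = 0.40, alpha = 0.10, beta = 0.20, early termination under the null 55.8%. From the précis: success at 40% or more, which is 10 or more of 25.

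**Formulas.** Let X1 ~ Bin(12, p) and X2 ~ Bin(13, p) be independent.

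- Early termination: P(X1 ≤ 2).
- Success with bar k: the sum over x = 3 to 12 of P(X1 = x) · P(X2 ≥ k − x).

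**Step 1: reproduce the plan's figures (k = 8).**

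- Early termination at p = 0.20: 0.0687 + 0.2062 + 0.2835 = 0.5583 (the unrounded terms give 0.55835). The plan states 55.8%.
- Type I error, success at p = 0.20: 0.0991. The plan states 0.10.
- Power, success at p = 0.40: 0.8151, so beta = 0.1849. The plan states 0.20.
- A search over designs with N up to 44 for the smallest expected sample size under p0, subject to alpha ≤ 0.10 and power ≥ 0.80, returns this design: stop at 2 or fewer of 12, fail at 7 or fewer of 25, expected N 17.7.

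The 8-of-25 rule is therefore the one that belongs to the stated design.

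**Step 2: apply the précis bar.** No section combines a bar of 10 with the first-stage gate, so this step is hypothetical. It shows what the précis sentence would mean if used as the rule.

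| Bar | Type I error (p = 0.20) | Power (p = 0.40) |
|---|---|---|
| ≥ 8 of 25 (10.1, 10.3) | 0.0991 | 0.8151 |
| ≥ 9 of 25 | 0.0445 | 0.7101 |
| ≥ 10 of 25 (précis, derived) | 0.0169 | 0.5686 |

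At 10 of 25, beta would be 1 − 0.5686 = 0.4314 against the stated 0.20.

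**Step 3: chance of a result on which the texts disagree.** This is the probability of passing stage 1 and ending at 8 or 9 of 25, which is the difference between the two success probabilities.

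| True rate | P(success, ≥ 8) | P(success, ≥ 10) | P(8 or 9 of 25) |
|---|---|---|---|
| 0.20 | 0.0991 | 0.0169 | 0.0821 |
| 0.30 | 0.4557 | 0.1861 | 0.2696 |
| 0.35 | 0.6580 | 0.3642 | 0.2938 |
| 0.40 | 0.8151 | 0.5686 | 0.2465 |

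The differences use unrounded values. At a true rate of 40%, 0.2465 / 0.8151 = 0.302, so 30.2% of the trials that succeed under 10.3 would not be positive under the précis.

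**The case against.** - **Section 10 governs in practice.** It is complete, and 10.1 and 10.3 agree on the count of 8. No sample size, interim decision or analysis depends on the précis sentence. This stands, and it limits the harm to reporting. But nothing in the document says which text prevails, and the sentence concerns the success criterion of the primary endpoint.
- **The précis may mean a true rate.** The figure equals p1, and the same bullet goes on to speak of finding the true response rate. The sentence itself does not say so. A rate that would make the study positive reads as a criterion on the result.
- **The labels differ.** The précis speaks of a positive study, 10.1 of clinical significance and 10.3 of sufficient interest for later trials. They could be different tiers, but section 10 defines no zone between 8 and 10 and gives no operating characteristics for a second bar.
- **The power loss is hypothetical.** This stands. Under 10.3 the trial has the power it claims. The practical measure of the conflict is the chance of landing on 8 or 9 of 25.
- **Section 10 is not uniform about the endpoint.** 10.1 counts stable disease of at least 16 weeks, while 10.3 and 10.5.1 write more than 16 weeks. This is true but separate. Leaving section 10 alone here means leaving its numerical cut-offs alone and does not settle the duration wording.

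**Conclusion.** The inconsistency is real and must be fixed. The précis bar is 10 of 25 and the section 10 bar is 8 of 25, so 8 and 9 of 25 are classified differently. The précis is the text in error, because only the 8-of-25 rule reproduces the stated error rates and the plan's 55.8%. The trial's design is not impaired: under 10.3 it has a type I error of 9.9% and power of 81.5%. The exposure is a disputed primary result, with probability 8.2% at a true rate of 20% and between 24.7% and 29.4% at the rates of 30%, 35% and 40%.

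These figures assume exactly 12 and 25 evaluable participants at the two looks, independent outcomes with a common rate, and the first-stage gate applied as written in 10.3. The count of 10 is derived from 40% of 25.

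**What to change.** 1. In the précis, replace the 40% sentence with: *Disease control in 8 or more of 25 evaluable participants would constitute a positive study (null rate 20%, target rate 40%).*
2. Word the précis gate to match 10.3: *3 or more of the first 12 evaluable participants with disease control.* The present wording omits the words for more than 3. It also uses response, which is narrower than disease control, since objective response (CR or PR) is a separate secondary endpoint in 10.1 and 10.5.3.
3. Date the correction and state in it that the cut-offs in 10.1 and 10.3 are unchanged. The documents do not say whether any result has been read, so the record should show that the rule was not moved.

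The cost is an edit to two sentences and a short dated note. Sample size, cut-offs, endpoint definition, data and participants are not affected.

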#### STATEMENT OF COMPLIANCE

The trial will be carried out in accordance with International Council for Harmonisation Good Clinical Practice (ICH GCP) and the following:

United States (US) Code of Federal Regulations (CFR) applicable to clinical studies (45 CFR Part 46, 21 CFR Part 50, 21 CFR Part 56, 21 CFR Part 312, and/or 21 CFR Part 812)

National Institutes of Health (NIH)-funded investigators and clinical trial site staff who are responsible for the conduct, management, or oversight of NIH-funded clinical trials have completed Human Subjects Protection and ICH GCP Training.

The protocol, informed consent form(s), recruitment materials, and all participant materials will be submitted to the Institutional Review Board (IRB) for review and approval. Approval of both the protocol and the consent form must be obtained before any participant is enrolled. Any amendment to the protocol will require review and approval by the IRB before the changes are implemented to the study. In addition, all changes to the consent form will be IRB-approved; an IRB determination will be made regarding whether a new consent needs to be obtained from participants who provided consent, using a previously approved consent form.

#### 1 INTRODUCTION

#### 1.1 STUDY OBJECTIVES

## 1.1.1 Primary Objective

 To determine the single agent antitumor activity (disease control rate) of the antisuperenhancer agent Minnelide in participants with advanced, previously treated ASCP

## 1.1.2 Secondary Objectives

- To determine the overall safety of Minnelide in participants with previously treated advanced ASCP
- To determine progression free survival (PFS) and overall survival (OS)

## 1.1.3 Exploratory Objectives

- Identify factors that influence participant response to treatment through detailed molecular analysis of participant tumor, serum and blood cell samples acquired at baseline, on-treatment and at time of progression
- Evaluate ctDNA as a marker of response in ASCP

#### 1.2 BACKGROUND AND RATIONALE

#### 1.2.1 Adenosquamous carcinoma of the pancreas (ASCP)

With a 5-year survival rate of <9%, pancreatic cancer is one of the most lethal types of cancer [1]. Every year about 55,000 people in the U.S. are diagnosed with pancreatic cancer, >90% of which have pancreatic ductal adenocarcinoma (PDA) [1]. It is now appreciated that there are at least 2 subtypes of PDA based on mRNA expression profiling: one that is more responsive to standard of care chemotherapy and has improved prognosis, and a second more aggressive type (variously termed squamous [2], quasimesenchymal [3] or basal-like [4]) that is highly refractory to standard chemotherapy and has a poorer overall survival [3-5]. Recently, it was appreciated that clades of

Version Date: 7/10/2025

the poor prognosis basal-like subtype can co-exist in a heterogeneous mix with better prognosis "classical" subtype areas within tumors of the same patient [6]. Although there are no normal cells within the pancreas that have a squamous differentiation, basal-like subtype tumors may have focal areas of morphologically squamous differentiation marked by expression of squamous markers p63, CK5 and CK6. Areas of squamous differentiation are absent from better prognosis classical subtype tumors. Hibayashi et al recently reported that the squamous differentiation areas appear to genetically evolve from regular glandular differentiation areas through mutation of a chromatin modifier gene (such as ARID1A, KMT2C) concurrent with amplification of MYC. Anti-tumor treatment with standard chemotherapy agents is anticipated to select for outgrowth of these chemoresistant areas with squamous differentiation.

Adenosquamous carcinoma of the pancreas (ASCP) is a rare variant of PDA that represents the extreme case of squamous differentiation. ASCP is histologically defined as a tumor containing both glandular and squamous differentiations with the squamous component constituting at least 30% of the tumor [7]. The arbitrary cutoff of 30% has been disputed in the literature [8, 9] with opponents noting that the evaluation is subjective and highly dependent on sampling [10] especially when fine-needle aspiration is used [11]. The reported prevalence of ASCP varies significantly in the literature ranging from 0.38% to 10% of all exocrine pancreatic cancers with most researchers reporting between 0.5% to 4% [12]. Pathologic diagnosis of ASCP is most straightforward in resected patients where the large quantity of tissue available allows for more conclusive determination of the percentage of squamous component in the tumor. Unfortunately, the majority of patients with ASCP do not present with resectable disease and diagnosis must be made from fine needle aspiration or core needle biopsy. Diagnosis using these methods is possible [13], however, definitive diagnosis of ASCP is more difficult as patients with some squamous component noted in the sample may be diagnosed with PDAC due to the pathologist's inability to conclusively quantitate a  $\geq$ 30% squamous component.

The prognosis for patients with ASCP is worse than for those with conventional PDA. In one 38-patient single institution study, the median survival of patients with resected ASCP was 10.9 months compared to 17.9 months for patients with PDA [6]. In another study comparing the survival of patients with all stages of ASCP to those with matched stages of PDA, the overall median survival for ASCP was about 5 months shorter than that for PDA (6.51 vs. 11.0 months) [11]. As in PDA, patients with ASCP are most often diagnosed too late for surgical resection and there are no effective treatments for advanced disease. Due to its relative rarity, there have been no published prospective clinical trials specifically treating patients with ASCP and no guidelines exist for treating patients with advanced ASCP. Case studies in the literature typically cite treatment regimens similar to those for PDA. As demonstrated by the poorer prognosis of ASCP patients compared to PDA, those treatments are not optimized for ASCP.

Because of the rarity of the disease, very few genomic profiling studies have been carried out on ASCP tumors. Until recently, our understanding of the molecular and genomic characteristics of ASCP was very limited. Fang et al. reported the whole genome and whole exosome sequencing of 17 ASCP tumors and found that prevalence of KRAS (100%) and p53 (88%) mutations exceeds that of PDA [14]. A previous report by Borazanci et al also identified *KRAS* mutation in 100% of ASCP tumor samples (16/16) [12]. Also similar to PDA, copy number variant (CNV) analysis revealed gains at 8q (*MYC*) and 12p (*KRAS*) and losses corresponding to the loci of *CDKN2A*, *TP53* and *SMAD4*. Interestingly, compared to PDA, ASPC had much more extensive and frequent chromosome 3p loss, which includes the *WNT5A* gene (5/11 PDA versus 16/17 ASCP), a

Version Date: 7/10/2025

chromosomal feature noted by the authors to also occur with high frequency in pure squamous cell carcinomas such as those of the head and neck, and lung [14]. More recently, Barrett et al described the genomic landscape of an additional 12 ASCP cases using tumor nuclei purified by a novel flow-sorting technique [15]. Frequent mutations in *KRAS* (92%, 11 of 12), *TP53* (83%) and *CDKN2A* (50%) were again noted, as well as frequent *MYC* amplification. As noted by Hibayashi et al, mutations targeting epigenomic regulators of chromatin organization were also common. These data support the theory that ASCP shares a common progenitor with PDA, but represents the most aggressive form of the disease, one that may evolve in PDA patients after multiple lines of standard treatment.

## 1.2.2 Minnelide, an anti-super enhancer drug that inhibits Myc

#### 1.2.2.1 Mechanism of action

Minnelide is a prodrug (14-0-phosponooymethyl triptolide disodium salt) of triptolide. It rapidly releases the active compound triptolide when exposed to phosphatase in the bloodstream. History of triptolide use and study is extensive since it is a diterpenoid triepoxide found in the Chinese plant *Tripterygium wilfordii*. For an extensive review of the agent, please see [16]. Multiple mechanisms of action for triptolide/Minnelide have been reported. Minnelide is known to inhibit HSP70 expression and to cause HSP-70-dependent apoptosis in pre-clinical models of PDA, a tumor type that typically overexpresses HSP70 [17]. However, triptolide may induce apoptosis in pancreatic cancer cells by different pathways depending on the cell line [18]. A summary table reporting anti-tumor efficacy of Minnelide in various pre-clinical models is shown below in Table 1

Table 1: Summary of Results in Primary Pharmacodynamic Studies with Minnelide™

Type of Study	Test System	Method of Administration	Results	Reference Number
Antitumor effect	Human pancreatic tumor cell lines			MN12- 001
Antitumor effect	Human A2780 ovarian tumor cell In vitro		"Activated" Minnelide™ inhibited ovarian tumor cell proliferation in a concentration-dependent manner.	MN12- 008
Efficacy – Orthotopic pancreatic tumor model	Athymic nude mice (Ncr nu/nu) implanted with MIA PaCa-2 tumor cells into the pancreatic tail	PO or IP	Once daily Minnelide TM treatment administered by the PO or IP routes were similarly effective at reducing tumor volumes and weights.	MN16- 001

Type of Study	Test System	Method of Administration	Results	Reference Number
Efficacy – Orthotopic pancreatic tumor model	Athymic nude mice (Ncr nu/nu) implanted with MIA PaCa-2 tumor cells into the pancreatic tail	IP; QD or BID	Minnelide™ treatment markedly improved animal survival and significantly decreased pancreatic MIA PaCa-2 tumor volumes and weights.	MN12- 002
Efficacy – Orthotopic pancreatic tumor model; comparison to gemcitabine treatment	Athymic nude mice (Ncr nu/nu) implanted with MIA PaCa-2 tumor cells into the pancreatic tail	Athymic nude mice (Ncr nu/nu) implanted with MIA PaCa-2 tumor cells into the pancreatic  Minnelide effective the decreasing PaCa-2 turn weights		MN12- 003
Efficacy – Orthotopic pancreatic tumor model	Athymic nude mice (Ncr nu/nu) implanted with S2-013 tumor cells into the pancreatic tail	with S2- cells into  IP; QD significantly decreased pancreatic S2-013 tumor volumes and weights, and markedly reduced the spread		MN12- 004
Efficacy – Orthotopic pancreatic tumor model	Athymic nude mice (Ncr nu/nu) implanted with AsPC-1 tumor cells into the pancreatic tail	IP; QD	Minnelide™ markedly improved animal survival and significantly decreased pancreatic AsPC-1 tumor volumes and weights even when daily treatment was initiated after palpable tumors were observed.	MN12- 005
Efficacy – Human pancreatic tumor xenograft model	SCID mice implanted subcutaneously with human pancreatic adenocarcinoma tumors	IP; QD	Minnelide™ markedly improved animal survival and significantly decreased tumor volumes and weights when daily treatment was initiated earlier (ATV~300 mm3) or later (ATV~1000 mm3) after tumor implantation.	MN12- 006
Efficacy – Spontaneous pancreatic tumor-forming mouse model	KRasG12D; Trp53R172H; Pdx-1 Cre mice	IP; QD	Minnelide™ treatment resulted in decreased tumor volumes and weights in animals genetically engineered to spontaneously develop pancreatic tumors.	MN12- 007
1 implanted		Minnelide™ markedly improved animal survival and decreased A2780 tumor volumes when administered daily, but not when administered twice or thrice weekly.		MN12- 008

Version Date: 7/10/2025

Type of Study	Test System	Method of Administration	Results	Reference Number
Efficacy – Subcutaneous pancreatic tumor model; dosing schedule comparison	Athymic nude mice (Ncr nu/nu) implanted subcutaneously with MIA PaCa-2 tumor cells	IP; QD or every third day	Minnelide™ significantly decreased MIA PaCa-2 tumor volumes when administered daily, but not when administered every third day.	MN13- 001
Efficacy – Minnelide™ in combination with gemcitabine plus abraxane (Gem/Abx)	Athymic nude mice (Ncr nu/nu) implanted with S2-VP10 tumor cells into the pancreatic tail	PO	Minnelide™ in combination with Gem/Abx was more effective than Minnelide™ or Gem/Abx treatment alone.	MN16- 002
Efficacy – Minnelide™ in combination with gemcitabine	Athymic nude mice (Ncr nu/nu) implanted subcutaneously with MIA-Paca2 or AsPC-1 tumor cells	IP	Combination treatment of Minnelide™ and gemcitabine was more effective than when the agents were administered alone.	MN16- 005
Efficacy – Minnelide™ in combination with paclitaxel	Athymic nude mice (Ncr nu/nu) implanted with S2- VP10 tumor cells into the pancreatic tail or subcutaneously into the flank  Minnelide™ with paclitaxe effective than alone.		Minnelide™ in combination with paclitaxel was more effective than the agents alone.	MN16- 003
Efficacy – Minnelide™ in combination with TRAIL	Athymic nude mice (Ncr nu/nu) implanted subcutaneously with S2-VP10 tumor cells	IP	Combination treatment of Minnelide™ and TRAIL was highly effective at doses of agents that were not effective when administered individually.	MN16- 004
Efficacy – Minnelide™ in combination with oxaliplatin	Athymic nude mice (Ncr nu/nu) implanted with MIA PaCa-2 tumor cells into the pancreatic tail	IP	Combination treatment of Minnelide and oxaliplatin was highly effective at doses of agents that were not effective when administered individually.	MN16- 006

